## C. Study Participants

**1. Inclusion criteria:** A set of standards will be used to determine which students are eligible to participate in the September 2021 randomized controlled trial (RCT):

A health student studying at MUHAS (as verified by being registered in one of the following classes):

- a. Year 2 and 3 nursing students (the final year but one or two where students have significant community and Clinical experience).
- b. Year 2 and 3 midwifery students (the final year but one or two where students have significant community and clinical experience).
- c. Year 3 and 4 medical students (the final year but one or two where students have significant community and clinical experience).
- d. Able to speak English and Swahili. Because the education seminars are in English, but history talks are in Swahili. Therefore all students must be able to understand and converse in English and Swahili.

**2. Exclusion criteria.** Students who meet the eligibility requirements above will be excluded from enrolling and participating in the RCT if::

- a. Students who will not be able to attend MUHAS on all days of the seminar
- b. If they are not available during the follow-up assessment dates.
- c. Students who express any reservations about attending (e.g., due to religious objections)
- d. Students who show fear of violence due to attending (e.g., from a spouse or relative).
- e. Students who are physically unwell during the RCT.
- f. Students who have a body temperature greater than 37.5 C.

**Procedure:** All enrollees are logged at enrollment with their name, student ID and contact details. If a student meets any of the exclusion criteria, their student ID and the reason why they were excluded will be logged.

**3. Number of participants to be enrolled for the RCT.** There will be 422 students enrolled for the September 2021 full trial: 412 of whom will be participants in the trial, plus 10 extra medical students to be waitlisted in case of absences.

- a. 284 medical students (which includes 274 confirmed participants and 10 waitlisted enrollees). Of these, 137 will be randomized to the control arm and 137 to the intervention.
- b. 103 nursing students. Of these, 52 will be randomized to the control arm and 51 to the intervention.
- c. 35 midwifery students. Of these, 18 will be randomized to the control arm and 17 to the intervention.

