#### 5. **Primary Dependent Variables.**

The following are the primary dependent variables:

- a. Knowledge is assessed using the 12-item knowledge quiz that is tailored to assess knowledge items taught in the curriculum.
- b. Attitude change: is from the SHEPS attitude/comfort scale
- c. Clinical skills are assessed using the clinical/expert raters review of the SP videos. See <https://link.springer.com/content/pdf/10.1023/A:1009878124073.pdf>.

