NCT03923582

R01HD092655

Title: Training for Health Professionals

Statistical Analysis Plan

Last updated: December 1, 2023

The intervention effect will be evaluated using a multiple regression analysis. The intervention group was assessed at baseline, immediately post-intervention, and follow-up, while the control group was assessed at baseline and follow-up only. Thus, difference scores (follow-up – baseline) will be calculated for each outcome listed above and used as the outcome for the regression models. "Intervention" (dummy coded as 0=control, 1=intervention) will be the primary predictor in the model. To assess whether there is a differential effect of intervention based on demographics, students' discipline, gender, and religious affiliation will be included as interaction effects (full model). In the current study, we recruited nursing, midwifery, and medical students. Due to the small number of midwifery students, midwives will be grouped with nurses for modeling purposes. Thus, discipline will be recoded into a variable called "Nursing" (0=medicine, 1=nurse/midwife). Similarly, gender will be coded as "Female" (0=male, 1=female) and religion will be coded as "Muslim" (0=Christian, 1=Muslim), based on the demographic groups with the most responses (demographic information was collected at baseline). If the interaction effects between Nursing, Female, and Muslim with Intervention are not statistically significant, the interactions will be removed from the model and the reduced model (without interaction effects but still including the main effects) will be fit and interpreted. All analyses will be run using R software (v 4.2.1).

Of the 412 recruited, one participant did not complete the post-intervention survey and three participants did not complete the three-month follow-up. Thus, these four participants will be removed from analysis. Furthermore, if participants did not identify as male/female or Christian/Muslim (e.g., responded "Other" or "Prefer Not to Answer"), they will be considered missing data and removed from analysis. Based on the demographic information collected at baseline, this will result in 396 participants for statistical modeling (96% of the total sample).

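### The SAP lets interaction tests choose the model and names no overall intervention effect if interactions are kept; the Intervention coefficient then describes male, Christian medical students

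*SAP*

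**What the plan says.** The SAP (first paragraph) analyses change from baseline to follow-up: "difference scores (follow-up – baseline) will be calculated for each outcome listed above and used as the outcome for the regression models". The treatment indicator "will be the primary predictor in the model". The full model adds its interactions with three indicators: Nursing (0 for medicine), Female (0 for male) and Muslim (0 for Christian).

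The selection rule is: "If the interaction effects between Nursing, Female, and Muslim with Intervention are not statistically significant, the interactions will be removed from the model". In that case, "the reduced model (without interaction effects but still including the main effects) will be fit and interpreted".

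The SAP has no matching sentence for significant interactions. It names no averaged effect, no centring and no set of subgroup estimates. It gives no significance level for the interactions. It does not say whether they are tested separately or jointly, or what happens when only one of the three is significant.

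The protocol does not fill the gap. Section I.5 introduces its list with "The following are the primary dependent variables" and names knowledge, attitude and clinical skills, but gives no analysis model.

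**The concern.** The trial asks whether the training works in health students as a whole. Under the SAP's rule, the data decide whether the main coefficient answers that question. In the reduced model it is one covariate-adjusted effect across all students. In a retained full model it is the effect in a single subgroup, estimated less precisely. Each outcome has its own regression, so the reported quantity could differ between primary outcomes.

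Two things are at stake. First, one chance interaction is enough to leave a primary outcome with no prespecified overall effect. Second, if the retained model's Intervention coefficient is reported as the result, the selection step raises type I error and lowers power when the training works equally well for everyone.

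**Working it through.** **Inputs from the documents**
- Analysis set: "this will result in 396 participants for statistical modeling" (SAP, second paragraph). Check: 412 − 4 non-completers = 408, so the gender and religion exclusions must number 408 − 396 = 12. 396/412 = 96.1%, which agrees with the SAP's 96%.
- Discipline (protocol, Section C.3): 274 medical students; nursing, "103 nursing students. Of these, 52 will be randomized to the control arm"; and 35 midwifery students. Nurse/midwife share = (103 + 35)/412 = 138/412 = 33.5%.
- Primary outcomes: three (protocol, Section I.5).

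**Assumptions, because the documents give no figure**
- Two-sided 5% tests; no true interaction; 30–50% women; 20–50% Muslims; uniform effect of 0.3 SD for power.
- Independent covariates, 198 per arm, and all three interactions kept after a switch.

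**1. Meaning of the coefficient.** In the full model the intervention effect is b1 + b5·Nursing + b6·Female + b7·Muslim. So b1 is the effect where all three indicators are 0: male, Christian, medical. This is algebra and needs none of the assumptions on shares or alpha.

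**2. Size of that group.** Share = (274/412) × (1 − female) × (1 − Muslim).
- 30% women, 20% Muslims: 0.665 × 0.7 × 0.8 = 37%, about 147 of 396.
- 50% and 50%: 0.665 × 0.5 × 0.5 = 17%, about 66 of 396.

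**3. Precision.** With 1:1 arms and independent covariates, SE ratio (full to reduced) = √(1 + Σ p/(1 − p)).
- 30%/20%: √(1 + 0.504 + 0.429 + 0.25) = √2.18 = 1.48.
- 50%/50%: √(1 + 0.504 + 1 + 1) = √3.50 = 1.87 (simulated 1.88).

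**4. Chance of a switch with no true interaction.**
- Per outcome, separate tests: 1 − 0.95³ = 14.3% (simulated 13.6–14.9%).
- Per outcome, joint 3-df F test: 5% (simulated 4.7–5.3%).
- At least one of three outcomes, separate tests: from about 14% (perfectly correlated outcomes) to 1 − 0.95⁹ = 37.0% (independent).
- At least one of three outcomes, joint test: from 5% to 1 − 0.95³ = 14.3%.

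**5. Error rates if the selected model's Intervention coefficient is read as the result.** Simulation, 12,000 trials per scenario, over female shares of 30, 40 and 50% and Muslim shares of 20, 30 and 50%:

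| | Reduced model always | Separate tests | Joint test |
|---|---|---|---|
| Type I error | 4.8–5.4% | 6.1–7.0% | 5.6–6.4% |
| Type I error among switched analyses | – | 14.6–17.5% | 21.6–27.1% |
| Power at 0.3 SD | 83.5–84.5% | 78.7–79.6% | 82.0–82.8% |
| Power among switched analyses | – | 44.6–50.9% | 45.1–53.9% |

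If only the significant interactions are kept, type I error is 6.8–9.0%.

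**6. When effects truly differ.** Take an average effect of zero and a 0.5 SD difference between nurse/midwife and medical students (4,000 trials per setting, separate tests). The selected coefficient is significant in 15–20% of trials, against about 5% for the reduced model. In this scenario the effect in medical students really is non-zero (−0.5 × 0.335 = −0.17 SD). The error lies in reading that subgroup effect as the overall one.

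**7. The alternative.** With mean-centred covariates, the full model's Intervention coefficient is the average effect. Its SE ratio to the reduced model is 1.000. Used after a switch on separate tests, it gives type I error of 4.7–5.0% and power of 84.1–84.9%.

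**The case against.** The strongest reply is that the SAP never says the retained model's Intervention coefficient will be reported as the trial result. It calls the intervention the primary predictor, which names a variable. It includes the interactions to look for differential effects, so a retained model would naturally be reported as subgroup effects. On this view the defect is one missing sentence, and the error rates above describe a misuse the plan does not prescribe. This is right as far as it goes: the type I error and power figures are conditional on that reading. But subgroup effects alone still give no overall effect, and the SAP does not ask for one.

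The size is also open to challenge. The unconditional inflation is one to two percentage points. The large figures for switched analyses apply, under a joint test, to about 5% of analyses: 0.05 × 22–27% is only about 1–1.5% of all trials. This stands.

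The male, Christian, medical reading requires all three interactions to stay. If only one stayed, the coefficient would refer to that factor's reference level alone, for example medical students. The SAP's contrast of a full with a reduced model favours keeping or dropping all three together, and the coefficient changes meaning either way.

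Selection outcome by outcome is the natural reading but is not spelled out. The outcome list to which the SAP refers does not appear in its text, so the count of three comes from the protocol.

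Independent covariates are a simplification. With 40% women, 30% Muslims and a female share in nursing 25 points above the overall share, the SE ratio falls from 1.61 to 1.52, and type I error with separate tests from 6.6% to 6.0%. Size changes; direction does not.

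**Conclusion.** The concern holds and should be fixed. The SAP makes the reporting of an overall effect depend on interaction tests and says nothing about the branch in which they are significant. With its 0/1 coding, the full-model Intervention coefficient then applies to an estimated 17–37% of the sample. These conclusions follow from the text and the algebra; only the percentage uses assumed gender and religion shares.

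The numerical harm is moderate. It arises only if that coefficient is taken as the result, and it rests on an assumed 5% level, assumed shares and independent covariates. The more important point is structural: by chance alone, between 5% and 37% of trials would have at least one primary outcome in the unspecified branch, depending on how the interactions are tested and how the outcomes correlate.

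**What to change.** - State that the main-effects model (Intervention, Nursing, Female and Muslim, without interactions) is the primary analysis for every primary outcome and is reported whatever the interactions show.
- Make effect modification a secondary analysis: one joint 3-df F test per outcome at a stated alpha, followed by subgroup effects with confidence intervals. Separate tests would also be defensible if prespecified; what matters is that they no longer choose the primary result.
- Wherever an interaction model is shown, report the average effect from it as well, using mean-centred covariates or marginal standardisation.

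The data, software and models stay the same, and precision is not lost (SE ratio 1.00). The SAP is dated December 1, 2023 and already reports follow-up completion, so the change should be a dated, disclosed amendment, with the analysis as now planned reported alongside.

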## **2. Consent the Participants**

**The consent form will describe:**

- a. Study purpose; (e.g., to evaluate a new sexual health training curriculum for MUHAS students)
- b. Tasks: The main tasks both have to be explicitly mentioned:
  - i. Taking 2-3 online surveys, one at baseline, one possibly immediately at the end of the training, and one at 3-month follow-up.
  - ii. Videoed simulated patient sexual history taking (to be assessed using Zoom recording of simulated intervention with standardized patients (SPs), at baseline and again in 3-months and to attend the seminar. This should include consent for video recording and the use of images for research and educational purposes.

- c. Risks (the primary one being emotional discomfort), limits on confidentiality, and benefits (none). Note: compensation should not be listed as a benefit)
- d. Practical details (e.g., detailed compensation) and what to do, and who to inform if they become ill during the study.
- e. Consent to be contacted at some future time for possible follow-up (if possible with a way to contact them for such follow-ups such as a cell phone number and non-MUHAS email address).

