**d. Two things happen at the end of the seminar.**

**i. post-seminar survey:** Immediately after the training, students remain in the room to complete online post-test surveys that measure the change in knowledge and attitudes, as well as a process evaluation of the training (30 minutes).

**Back-up plan:** Should there be internet connection issues on the last day of training, then three study staff will be responsible persons for distributing and collecting paper copies of the surveys, and ensuring that all questions are filled out correctly. This will not be the case for online Qualtrics surveys since the survey will be programmed in a way that will minimize incomplete responses and data entry errors.

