d. **Individual withdrawal from the Study.** This study is voluntary, therefore if anyone chooses to withdraw from the study, study staff will allow them to do so. Anyone notifying the study that intends to not attend the rest of the training shall be referred to **Project Coordinator**. **Project Coordinator** will review the intent of the participant and any reason why they will not be continuing in the training. Depending on the reason (e.g., sickness, family emergency, the decision to withdraw), he will thank them for informing the study of this decision, inform them that they will be compensated for the days attended but not days not attended, and will record the reason given why the participant dropped out of the study. Finally, **Project Coordinator** will ask if the participant is dropping out of the training only, or is wishing to drop out of the study. (NOTE: If a participant drops out of the training, they are still considered a participant and we prefer them to complete the post-seminar evaluation and the follow-up even if they missed part of the training).

2. **If a student misses a survey, what happens?** If a student is missing the baseline survey and/or the SP evaluation, he/she will not be allowed to participate in the training. Instead, his/her place will be given to one of the students on the waitlist.

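### Minor: the SAP excludes one student for missing a survey that only the intervention arm took and the model does not use; separately, 12 students need not be lost over gender or religion coding

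*SAP*

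**What the plan says.** The SAP (first paragraph) takes as outcome the difference between follow-up and baseline. It explains that the intervention group was measured three times, "while the control group was assessed at baseline and follow-up only". Its second paragraph starts from 412 recruited. It reports that "one participant did not complete the post-intervention survey" and that three others lack the three-month follow-up, and then states: "Thus, these four participants will be removed from analysis".

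The same paragraph deals with students whose gender or religion falls outside the two coded levels: "they will be considered missing data and removed from analysis". The resulting modelling sample is 396, given as 96% of the total. If the interactions are not significant, the model that is interpreted is the one "without interaction effects but still including the main effects", so gender and religion stay in it.

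The protocol (section H.2.d) places the post-seminar survey at the end of the training, when "students remain in the room to complete online post-test surveys". Section H.3, on individual withdrawal, gives the retention intent: "If a participant drops out of the training, they are still considered a participant".

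**The concern.** Two exclusions deserve a look, and they differ in kind.

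1. **The post-intervention survey.** A control student cannot miss a survey that controls were never given. The criterion therefore operates after assignment and in one arm only. The measurement it depends on is not part of the modelled difference score. The SAP gives the absence of this measurement in controls as its reason for using follow-up minus baseline, so requiring it for inclusion runs against the SAP's own reasoning. At stake is a clean definition of the analysis set: a one-arm exclusion based on unused data is hard to defend, even for one person.

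2. **Gender and religion coding.** Students outside the coded levels cannot contribute to the Female and Muslim interaction tests. They can contribute to the average intervention effect, but the reduced model keeps both main effects with the same coding, so they are lost there too. At stake are a little precision and a slightly narrower population.

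**Working it through.** **Reproducing the SAP's count.** Inputs from the SAP, second paragraph: 412 recruited, 1 without the post-intervention survey, 3 without follow-up, 396 modelled.

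- 412 − 1 − 3 = 408, reading the four as distinct people, as the SAP does.
- 408 − 396 = 12 removed for gender or religion coding. The SAP does not print this number or split it by arm.
- 396/412 = 96.1%, which agrees with the stated 96%.
- 12/408 = 2.9%.

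**Counts after the changes.**

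| Situation | N |
|---|---|
| Student in (1) has baseline and follow-up and is codable; the 12 still out | 396 + 1 = 397 (96.4% of 412) |
| Student in (1) has no follow-up; the 12 still out | 396 |
| Student in (1) has both; the 12 kept in the main-effects model | 412 − 3 = 409 |
| Student in (1) has no follow-up; the 12 kept | 412 − 4 = 408 |

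**Effect of the one student.** The planned intervention arm (protocol, section C.3) is 137 + 51 + 17 = 205. If the student's difference score lies k SD from the mean of the rest of the arm, including the student moves the arm mean, and so the contrast, by k/205. The documents give no value for k; I assume 0.5 to 3.

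- k = 0.5: 0.5/205 = 0.0024 SD
- k = 3: 3/205 = 0.0146 SD

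With SD 1 and equal arms (assumed), the standard error of the difference is 2/√n, which is 0.0989 at n = 409. The shifts are then 0.0024/0.0989 = 0.02 and 0.0146/0.0989 = 0.15 of one standard error.

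**Precision.** On the same assumptions:

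- 2/√396 = 0.1005; 2/√397 = 0.1004; 2/√409 = 0.0989
- √(397/396) = 1.0013: the one student is worth 0.13%
- √(409/397) = 1.015: the 12 alone are worth 1.5%
- √(409/396) = 1.016: both together are worth 1.6%

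These figures ignore the cost of fitting two sparse extra levels. A simulation of 4,000 data sets included Intervention, Nursing, Female and Muslim, with the 12 split at random over an extra level for gender and one for religion. Nursing or midwifery was set at 138/412 (protocol, section C.3: 103 + 35). Female at 0.45 and Muslim at 0.30 are assumptions. The mean standard error was 0.0995 at 409 with the extra levels, 0.1008 at 397 and 0.1009 at 396. The ratios to 409 are 1.013 and 1.014. A fair range for the gain is therefore about 1.3 to 1.6%.

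**The case against.** The strongest objection is that the SAP never says the student who missed the post-intervention survey came back at follow-up. If losses were counted by stage, this student may have left at the post-intervention stage, with three more lost later. No difference score would then exist, nobody would be wrongly excluded, and 396 would stand. This objection holds as far as it goes. Counting the student apart from the three without follow-up suggests that follow-up data exist, but does not establish it. The criterion itself is still wrong for the stated model, and under this reading the stated reason for exclusion needs correcting.

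A reader might also infer more from the protocol than it offers. The consent section (G.2) describes the survey as "one possibly immediately at the end of the training", which could be taken to mean that it was optional. The consent form is signed before students learn their assignment, so the natural meaning is that only those assigned to the training take it. Likewise, the note in H.3 concerns students who leave the training and states a preference that they complete later assessments. It shows the intent to retain people; it does not define an analysis set, and nothing says this student left the training.

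It can also be said that a complete-case set across all three time points was intended for some other analysis. The SAP text refers to an outcome list that does not appear in it, so the criticism is confined to the model that it does describe.

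On the 12, the objection is that the rule is explicit, rests on baseline answers and treats both arms alike. That is correct, and it is why this part is not called an error.

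**Conclusion.** Minor on both counts.

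1. The post-intervention-survey criterion should go. It is a one-arm, post-assignment exclusion on data that the stated model does not use. Whether it actually removes a usable student depends on that student having both baseline and follow-up, which is implied but not stated. If so, the effect on the contrast is about 0.002 to 0.015 SD, given the assumed distance of 0.5 to 3 SD and the planned arm of 205.

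2. Dropping the 12 from the main-effects model is a small, avoidable loss, worth about 1.3 to 1.6% in standard error. The range rests on equal arms, unit SD and assumed gender and religion prevalences.

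A reader might conclude that these exclusions bias the trial's result. The documents do not support that. The first concerns at most one student and moves the estimate by a small fraction of a standard error. The second uses baseline answers in both arms and does not bias the contrast. Neither is likely to change the conclusion.

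**What to change.** - Define the analysis set for each outcome as students with both baseline and follow-up on that outcome, and delete the post-intervention-survey criterion.
- Check the one student's records. If baseline and follow-up are both present, keep the student and restate the N: 397 if gender and religion are also codable. If follow-up is missing, leave 396 and correct the stated reason.
- In the main-effects model, keep the other 12 through an additional other-or-undisclosed level for gender and for religion. This gives up to 409 for survey outcomes, or 408 if the student above lacks follow-up. Restrict only the interaction models to students codable on both factors.
- Report exclusions by arm and reason for each analysis.

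The cost is SAP wording, two extra factor levels and one table; no new data are needed. The drawbacks are sparse levels and different Ns across analyses. A level holding a single student, or students from one arm only, adds nothing to the contrast.
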